STUDY PROTOCOL & STATISTICAL ANALYSIS PLAN

Official title: MOTIVATE: Moving to Improve Chronic Back Pain and Depression in Older Adults

NCT number: NCT03914469

IRB Approved date: 06-10-21

The University of Texas Southwestern Medical Center at Dallas Institutional Review Board

Title: MOTIVATE: Moving to Improve Chronic Back Pain and Depression in

Older Adults

Principal Investigator: [name]- Principal Investigator

Funding Source: Institutional funds

Purpose and Objectives

The overarching goal of this study is to evaluate a tele-based behavioral change intervention for older adults (aged 50 years and older) with chronic low back pain (cLBP) and comorbid depression, and to ultimately assess its effect on cLBP-related disability and depressive symptoms.

Specific Aims: Behavioral interventions for older adults with comorbid chronic low back pain (cLBP) and depression are urgently needed. Our group developed a telephone delivered intervention targeting behavioral constructs common to both cLBP and depression in older adults: MOTIVATE (Moving to Improve Back Pain and Depression in Older Adults). Further, we emphasize individualized values, goals and motivations to change behavior- all relevant for sustaining behavior change. We now seek to 1) evaluate the feasibility of MOTIVATE in a diverse older adult population, and 2) inform future research and trial design choices by eliciting feedback from key stakeholder groups. These results will inform methods and procedures for use in a large-scale, R01 level hybrid (Type 1) effectiveness-implementation randomized controlled trial (RCT).

Aim 1: Evaluate the feasibility of implementing MOTIVATE (n=25) vs. waitlist control (n=25) among older adults with comorbid cLBP and depression.

Aim 2: Ascertain key barriers and facilitators to implementing MOTIVATE in a diverse older population in primary care. We will conduct semi-structured interviews with 10 participants, 5 clinicians, and the health coach, to explore factors critical to eventual uptake of MOTIVATE, e.g., acceptability, adoption, sustainability.

Background and Current Practice

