In aim 1, we will assess the feasibility of a tele-delivered behavioral change intervention among older adults (aged 50 and older) with cLBP and depression. Fifty participants will be randomly assigned to one of two groups, behavioral intervention arm (n=25) versus the waitlist control arm (n=25). The active intervention will include eight tele-delivered health coach sessions and three tele-based outcome assessments. Each tele-based outcome assessment is roughly 45-60 minutes, and will be conducted by a member of the research team and will be recorded for research purposes. Each intervention session will be delivered by a trained health coach over a period of 10-20 weeks (up to 5 months total, accounting for additional time between sessions if needed). Aim 2 will involve one, in-depth, telephone-based, semi-structured interview at 6 months post-intervention. The health coach/research coordinator will identify participants who are at higher risk for drop-out, less engaged, or particularly successful at achieving behavioral change. The purpose of this interview is to learn about the barriers and facilitators to successful intervention delivery and integration within primary care, participant retention and acceptability from the clinician, patient, and health coach perspective. We will explore factors that are critical to eventual uptake of MOTIVATE; informed by Proctor's Framework of Implementation Outcomes we will focus on acceptability, adoption, appropriateness and sustainability of MOTIVATE. Semi-structured interviews with patients will be occur over the telephone, while clinician semistructured interviews can occur over the telephone or at a location convenient for the participant-most likely to occur on a UTSW or Parkland location.

The first session will introduce the participant to the health coach and the program, establish rapport, and measure baseline physical activity. The following six sessions address behavioral determinants, followed by a final session designed to be a booster session to the overall program.

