Study data will be stored within password protected data management programs, on password protected computers. Only IRB approved study personnel will have access to study data. All research staff will be trained in the appropriate safeguarding of confidential data and in the protection of human participants. At the end of the study, after analyses are complete, all study data will be de-identified, and the identifying key will be destroyed per UTSW and Parkland policies and regulations. The health coach will have restricted access to the study database; he/she will also have access to EMR as needed.

Outcome Assessments and Data Collection

Using age >50, ICD-10 codes for chronic back pain and depression as criteria, an initial data pull from patients' EMR will yield a list of potentially eligible prospective study participants. The research team will pre-screen this list of potentially eligible patients for recruitment. As outlined in section **Recruitment Strategy and Informed Consent Process**, participant recruitment may occur in-person or by tele-based method and will include an introduction to the study and **verbal consent**. Upon completion of consent, a research staff member will further screen for eligibility and arrange a separate telephone call for a baseline assessment. As seen in the **Figure 2** below, a research team member, not the health coach, will complete all outcome assessments via telephone using structured data collection tools at baseline, midpoint (~ 5 weeks), end-point (~ 10 weeks), and 6 months post-intervention. A subset of the participants from the trial will be invited for an in-depth, semi-structured interview, as discussed above (Aim 2), to better understand implementation and sustainability of behavior uptake.

All study-related data from the assessments will be entered into a UTSW REDCap database at: https://ais.swmed.edu/redcap/. Only de-identified data will be entered in REDCap. The health coach or a research staff member will obtain daily versus weekly step counts from study participants as appropriate depending on the session content and activity tracker assignment.

Outcome Measures

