 their associated diagnosis/procedure codes (which our research team will use to determine if pain,
 degenerative joint disease, depression-related).

Table 2. Demographic and Clinic	al Data Poin		come Asses	sment Instr	ument	5
DATA	SOURCE	PRE- SCREEN	SCREEN	BASELINE	MID	END
Sex	EMR	Х		Х		
Age 50+	EMR	Х		Х		
ICD-10 back pain	EMR	Х				
ICD-10 depression	EMR	Х				
History of suicidal ideation	EMR	X				
Psychotic or suicidal hospitalization w/ past year	EMR	Х				
Telephone	EMR	Х				
	Phone					
Inclusion/Exclusion Criteria						
50 or older (confirm)	Phone		Χ			
(Clbp confirm) Low back pain (+/-radiation) on most days for the past 3 months?	Phone		Х			
(Clbp confirm) Does your back pain limit your ability to do activities around the home or activities that you enjoy?"	Phone		Х			
Rate pain level in past week (Scale 0-10)	Phone		Х	Х	Х	Х
Self-report hearing/visual challenges	Phone		Х			
Lumbar surgery within past year	Phone		Χ			
Recent illness/diagnosis of concern	Phone		Х			
Bed bound	Phone		Х			
Use of wheelchair around the house	Phone		Х			
Safety & Physical Activity	Phone		Х			
Cognitive Screener	Phone		Х			
Patient Health Questionnaire (PHQ-9)	Phone		Х	Х	Х	X
Self-Report Demographics and Other	Clinical Vari	ables				
Race/Ethnicity	EMR Phone			Х		
Education	EMR Phone			Х		
Marital Status	EMR Phone			Х		
Living situation	EMR Phone			Х		
Address	EMR Phone			Х		

Charleston Age Comorbidity	EMR	Х		
Calculator				
Body mass index	EMR	Х		
Medication list	EMR	Х		
	Phone			
Pain injections at ER/outpatient in	EMR	Х	Х	Х
the last month				
Med/mental/PT appointments	EMR	Х	Х	X
(related to Clbp/depression) or	Phone			
ED/urgent care visits within the last				
6 months				
Financial situation	Phone	Х		
Most frequented primary care clinic	Phone	Х		
location				
Short Michigan Alcoholism	Phone	Х		Χ
Screening Test (SMAST)				
Drug Use Questionnaire (DAST)	Phone	Х		
Expectation of Intervention	Phone	X		
Pain Screen Tool (PEG)	Phone	X	Х	Χ
Self-Efficacy Arthritis	Phone	X	Х	Х
Roland Disability Quest: Rating	Phone	Х	Х	X
Scale for Low Back Pain				
Pain Catastrophizing Scale (PCS-EN)	Phone	X	Х	Х
Fear Avoidance Beliefs	Phone	Х	Х	X
Questionnaire (FABQ)				
Physical Activity Contemplation	Phone	Х	Х	Х
Ladder				
Exercise Questionnaire	Phone	Х	Х	Χ
General Health Questions	Phone	X	Х	Х
Pain Stage of Change	Phone	Х	X	Χ
PROMIS 1.2 Global Mental Health	Phone	Х	X	Χ
PROMIS 1.2 Global Physical Health	Phone	Х	Х	X
PROMIS SF 1.1 Pain Behavior	Phone	Х	X	Χ

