Proposed Analyses

Exact binomial method will be used to estimate rates of recruitment, intervention adherence, retention, and drop-out along with the corresponding 95% confidence intervals. Multiple levels of treatment retention will be defined, including partial intervention completion (% who do not complete all sessions), intervention dropout (% who dropout of intervention but continue to do assessments), research dropouts (% who remain in intervention, but do not complete assessments), and intervention + research dropouts (% who do not complete intervention or assessments). We will further break down the enrollment and retention calculations by examining enrollment/retention differences by treatment group, health coach, sex, age, race/ethnicity, and initial cLBP and depression severity using cross-classification tables.

As exploratory analyses, pre- and post-improvement in disability (RMDQ) and depression (PHQ-9) scores, as well as secondary and intermediate outcomes, from baseline to three months will be compared based on a two-sample t-test or Wilcoxon rank-sum tests between the two groups. The difference in improvement will be estimated and the 95% confidence interval will be reported. We will

estimate the preliminary effect size and variance of effect for the above outcomes. Linear mixed models will be used to assess whether there is a difference in the above outcomes over time within and between the two groups. We will include distance (in miles) from a UTSW or Parkland facility as a covariate in the exploratory outcome analyses, as suggested by reviewer.

We will describe, for the subset of participants receiving the intervention, whether physical activity (proximal outcome) and clinical outcomes (disability and depression scores) change over time based on the 1) proportion of the total sessions completed, and 2) the proportion of individual sessions completed. This will help us estimate optimal dose of the intervention (for example, whether completion of 4 vs. 7 vs. 8 of 10 sessions produces similar outcomes) and may inform which specific sessions are absolutely critical. SAS (version 9.3, Cary, NC) statistical software will be used.

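### Enrolment is to be compared by race/ethnicity, but race/ethnicity is scheduled only at baseline, so the comparison has no values for people who do not enrol

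*Combined protocol and SAP*

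**What the plan says.** Specific Aims sets out to "evaluate the feasibility of MOTIVATE in a diverse older adult population". Feasibility Outcomes names enrolment rates across the two health systems, adherence and retention, and says the results are to inform a fully powered trial.

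Proposed Analyses states: "Exact binomial method will be used to estimate rates of recruitment, intervention adherence, retention, and drop-out along with the corresponding 95% confidence intervals". It does not say whether the denominator of the recruitment rate is patients listed, invited, screened or eligible. It then plans to break the calculations down by "examining enrollment/retention differences by treatment group, health coach, sex, age, race/ethnicity, and initial cLBP and depression severity using cross-classification tables".

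Table 2 says when each variable is collected:

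- Sex and age: EMR, at PRE-SCREEN and again at BASELINE.
- "Race/Ethnicity": source EMR and phone, at BASELINE only.
- The 0–10 pain rating and the PHQ-9: phone, first at SCREEN, then at BASELINE, MID and END.

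Outcome Assessments and Data Collection gives the order of events: "Upon completion of consent, a research staff member will further screen for eligibility and arrange a separate telephone call for a baseline assessment".

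**The concern.** Enrolment by subgroup is a ratio: those enrolled from the group, over those in the group who could have enrolled. The numerator comes from the baseline data. The denominator needs the group recorded for people who used the refusal number in the invitation letter, were never reached, declined, or failed screening. Table 2 does this for sex and age but not for race/ethnicity.

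Race/ethnicity is the breakdown variable most directly tied to the aim of a diverse population. Without denominators, the study cannot separate a group that was rarely listed from one that was listed but declined or was screened out. Those two findings call for different changes in the larger trial: different sites or search criteria in the first case, a different approach or different eligibility screening in the second.

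**Working it through.** The documents give no figure to reproduce, and the point concerns which data exist. The check is to set the schedule against the planned analysis and then show by illustration what the missing denominator does.

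**Step 1: who has a value for each breakdown variable, as scheduled in Table 2.**

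| Variable | First scheduled | Non-enrolled patients with a value |
|---|---|---|
| Sex, age | PRE-SCREEN (EMR) | All on the EMR list |
| Pain rating, PHQ-9 | SCREEN (phone) | Those screened but not enrolled |
| Race/ethnicity | BASELINE (EMR, phone) | None who stop before baseline |
| Treatment group, health coach | After eligibility and randomisation | Not applicable |

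Enrolment by sex and age can be computed for listed patients. Enrolment by severity can be computed among screened patients. Enrolment by race/ethnicity cannot be computed from what is scheduled. The table was read from text extracted from PDF, so column positions deserve a check against the original, but the race/ethnicity, pain and PHQ-9 rows read cleanly.

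**Step 2: what the enrolled mix alone can show.**

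Input from the documents: 50 randomised (Study Design). Assumptions: 20 of the 50 belong to group A; the pre-screen list has 250 patients; group A makes up 30%, 40% or 60% of it.

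The share of A among the enrolled is 20/50 = 40% (exact 95% CI 26% to 55%), and it is the same in every row below.

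Rate in A = 20 / (250 × share). Rate in the rest = 30 / (250 × (1 − share)).

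| Share of A on list | Rate in A | Rate in the rest | Ratio |
|---|---|---|---|
| 30% | 20/75 = 26.7% | 30/175 = 17.1% | 1.56 |
| 40% | 20/100 = 20.0% | 30/150 = 20.0% | 1.00 |
| 60% | 20/150 = 13.3% | 30/100 = 30.0% | 0.44 |

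With a list of 500 the rates halve and the ratios stay the same. Identical baseline data therefore fit over-enrolment, equal enrolment and under-enrolment of group A.

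**Step 3: precision once denominators exist.**

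For the 250-patient list, the exact 95% intervals are:

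- 30% share: 17.1% to 38.1% against 11.9% to 23.6%. These overlap.
- 60% share: 8.3% to 19.8% against 21.2% to 40.0%. These do not overlap.

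Denominators would make the comparison possible. They would not make it precise in every case.

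**The case against.** The strongest reply is that this is one missing mark in a schedule. Race/ethnicity already has the EMR as a source, Participant Selection plans an EMR pull before any contact, and Database Management says REDCap tracks screening and recruitment. The data are unscheduled, not unobtainable. That stands, and a reader who inferred that the trial cannot show whom it reaches would go too far. But no section says race/ethnicity is kept for people who do not enrol. Procedures to Maintain Confidentiality has identifiers destroyed after study completion, so later recovery should not be relied on.

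A reader might also infer that enrolment by initial severity fails in the same way, because severity is known only after consent and merely repeats the entry thresholds. The documents do not support that. Pain and PHQ-9 are taken at SCREEN, so people screened but not enrolled have values, and severity varies widely above the thresholds (pain 4 to 10, PHQ-9 above 10). The timing relative to consent is itself unsettled. Outcome Assessments and Data Collection puts consent first. The recruitment section seeks a consent waiver that covers screening, the Parkland strategy screens after opt-out letters, and the PHQ-9 criterion mentions chart review. These sections should be reconciled.

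Listing treatment group and health coach under enrolment is best read as compressed wording: the two apply to retention. Retention by race/ethnicity works as planned.

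It is also fair to say that the aim speaks of feasibility in a diverse population and does not explicitly ask for reach by race, and that the make-up of the enrolled sample does describe its diversity. However, the analysis section itself promises the enrolment comparison. Finally, small numbers limit what it can show. If 15 of 50 enrolled came from a group that was 200 of 500 listed, the rates would be 7.5% against 11.7%, with overlapping exact intervals (4.3% to 12.1% and 8.3% to 15.9%). That argues for reporting it descriptively, not for omitting the denominator.

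**Conclusion.** The point holds in a narrow form. Enrolment by race/ethnicity is planned, but as scheduled it has no values for patients who stop before baseline, so only the mix of those enrolled can be reported. On the assumed figures, one enrolled mix fits enrolment-rate ratios from 0.44 to 1.56. The list size and group shares behind that range are assumptions, and the conclusion about missing values does not depend on them. Sex and age, severity among screened patients, and every retention breakdown are unaffected. The change is worth making because it is cheap and bears on a stated goal. It does not threaten the trial's other feasibility results.

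**What to change.** 1. In Table 2, mark race/ethnicity (EMR) at PRE-SCREEN for every listed or referred patient, and keep the baseline phone confirmation.
2. In Proposed Analyses, state enrolment and retention separately.
   - Enrolment by sex, age, race/ethnicity and health system, with the denominator given for each recruitment route (EMR list, provider referral, flyer). Flyer callers and referred patients may not be on the EMR list, so one pooled denominator would not serve. Health system belongs here because Feasibility Outcomes already names enrolment across both.
   - Enrolment by initial severity only among screened patients who meet the pain and PHQ-9 entry thresholds, labelled as such.
   - Retention among randomised patients by all the variables already listed, including sex, age and race/ethnicity. Treatment group and health coach apply to retention only.
3. Do the extraction before identifiers are destroyed.

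The cost is one more field in an EMR pull already planned, plus rewording. The downsides are that EMR race/ethnicity is less complete than self-report and that the pre-screen data request widens slightly.

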For aim 1 researchers will collect relevant demographic and clinical data either from patient EMR data abstraction or directly from the participant during a tele-delivered session. The research team will also collect various data points at specific intervals throughout the study duration using REDCap outcome assessment tools. A description of outcome assessment tools are included below. For aim 2, researchers will ascertain key barriers and facilitators to implementing MOTIVATE in a diverse older population in primary care and will explore factors critical to eventual uptake of MOTIVATE, e.g., acceptability, adoption, sustainability. The in-depth, semi-structured interviews will include a discussion guide with prompts focusing on acceptability, adoption, appropriateness, and sustainability of implementing MOTIVATE with older adults in primary care. All of these categories are relevant to patients, clinicians, and leadership, though nuances will emerge during interviews. We will stop conducting interviews once we reach thematic saturation and no further responses/ themes are provided.

Feasibility Outcomes

Feasibility outcomes, including recruitment and fidelity, will be collected and are intended to inform future grant proposals for a fully powered hybrid effectiveness/implementation award. All health coaching tele-sessions will be audio recorded using a telephone recording adapter (Model: LRX 40 USB) or audio recorders built into the telephones in DPDS. 20% of study sessions will be assessed using a fidelity checklist to ensure that the intervention is being delivered as intended. The fidelity checklists will be submitted along with this IRB. The purpose of the fidelity checklists is to verify that the objectives and core concepts for each session are being delivered as intended to the participants. Feasibility outcomes include, enrollment rates across GIM primary care and Parkland internal medicine/primary care clinic or community outpatient clinics, intervention adherence (measured as number of sessions the participant engaged in), and retention rate.

Primary outcomes for future effectiveness trial will be assessed:

- Physical function/ self-reported disability will be measured by the Roland Morris Disability Questionnaire (RMDQ). The RMDQ is valid, reliable and responsive to change in community dwelling patients with cLBP. Pain disability is important because this is a major treatment target in patients with chronic pain.

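### The RMDQ and PHQ-9 group difference is planned as an unadjusted change score, and the mixed model's handling of baseline is left open; baseline adjustment would usually give a modestly narrower interval

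*Combined protocol and SAP*

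**What the plan says.** Proposed Analyses labels the outcome comparisons exploratory. Improvement in RMDQ, PHQ-9 and the other measures "from baseline to three months will be compared based on a two-sample t-test or Wilcoxon rank-sum tests between the two groups". Next comes this sentence: "The difference in improvement will be estimated and the 95% confidence interval will be reported". The plan will then "estimate the preliminary effect size and variance of effect for the above outcomes".

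Two further sentences bear on the same measures: "Linear mixed models will be used to assess whether there is a difference in the above outcomes over time within and between the two groups", followed directly by "We will include distance (in miles) from a UTSW or Parkland facility as a covariate in the exploratory outcome analyses". Distance is the only covariate named. No outcome analysis mentions the baseline score as a covariate, and nothing says whether baseline enters the mixed model as an outcome, as a covariate or as a mean common to both arms.

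Both scores are collected at baseline. In Table 2 the row beginning "Roland Disability Quest: Rating" has three marks, read here as baseline, mid and end. PHQ-9 is marked at screening and at those three assessments. Outcome Measures introduces RMDQ and PHQ-9 with the words "Primary outcomes for future effectiveness trial will be assessed". Study Procedures allocates 25 participants to each arm.

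**The concern.** A change score gives the baseline value a fixed weight of one. Regression on baseline estimates that weight from the data, and in a randomised comparison this usually leaves less residual variance. The plan collects the baseline score and intends to fit models that can carry covariates, yet the comparison it describes does not use baseline in this way.

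No efficacy claim depends on this, because the pilot's main aim is feasibility. What is at stake is the width of the interval, and the clarity of the preliminary effect size and variance, for two outcomes that the protocol earmarks as primary in a later effectiveness trial.

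**Working it through.** The documents give no SD, correlation or effect size for RMDQ or PHQ-9, so there is no stated figure to reproduce.

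**Inputs.** From the documents: 25 per arm (N = 50) and a 95% interval. Assumed: correlation rho between baseline and follow-up of 0.4, 0.5, 0.7 or 0.8; equal SDs, set to 1; complete data; distance unrelated to outcome.

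**Formulas.**
- Change score, variance per participant: 2(1 − rho).
- Adjusted, variance per participant: (1 − rho²) × (N − 3)/(N − 3 − p), with p covariates besides arm. At N = 50 the factor is 47/46 for baseline alone and 47/45 for baseline plus distance.
- Half-width: t × √(2v/25), with t = 2.011 on 48 df (change) and 2.013 on 46 df (baseline plus distance).

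**Example, rho = 0.5.** Change: v = 1.00 and half-width 2.011 × √(2/25) = 0.569. Adjusted for baseline and distance: v = 0.75 × 47/45 = 0.783 and half-width 2.013 × √(2 × 0.783/25) = 0.504. The ratio is 0.504/0.569 = 0.89, so the interval is 11% narrower.

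| rho | Variance ratio, baseline only | Variance ratio, baseline + distance | Half-width in SD units, change to baseline + distance | Narrower by |
|---|---|---|---|---|
| 0.4 | 0.72 | 0.73 | 0.62 to 0.53 | 14% |
| 0.5 | 0.77 | 0.78 | 0.57 to 0.50 | 11% |
| 0.7 | 0.87 | 0.89 | 0.44 to 0.42 | 6% |
| 0.8 | 0.92 | 0.94 | 0.36 to 0.35 | 3% |

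Simulation with normal data (40,000 trials per rho) gave variance ratios of 0.740, 0.783, 0.891 and 0.945 with distance in the model. Both methods had a mean estimate of about zero and coverage of 0.95. With 20 per arm (assumed loss) the gains are 14, 11, 5 and 2%.

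**Does the mixed model already deliver this?** Take three visits, compound symmetry with known covariance and complete data. The variance of the end-point contrast, in units of 2/n, for rho 0.4, 0.5, 0.7 and 0.8 is:
- separate baseline means: 1.20, 1.00, 0.60, 0.40, equal to 2(1 − rho), the change score;
- common baseline mean: 0.84, 0.75, 0.51, 0.36, equal to 1 − rho², ANCOVA before the covariate cost.

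The gain therefore depends on a choice that the plan does not make.

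**Unequal SDs.** With k = follow-up SD / baseline SD, the baseline-only ratio is k²(1 − rho²)(47/46)/(1 + k² − 2·rho·k). At k = 1.2 it is 0.84, 0.89, 0.99 and 1.02; at k = 0.8 it is 0.55, 0.58, 0.64 and 0.65. The denominator equals (1 − rho·k)² + k²(1 − rho²), so before the covariate cost the ratio cannot exceed 1. The worst case is thus 47/46 = 1.02, or 47/45 = 1.04 with distance.

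**PHQ-9.** The Inclusion Criteria require a screening PHQ-9 above 10. As an illustration, assume normal scores, selection above the mean of the screening score, a screening to baseline correlation q = 0.85, and follow-up related to screening only through baseline. Here rho is the correlation before selection. Selection removes a share s = (2/π)q² = 0.46 of the baseline variance. The adjusted variance stays at 1 − rho², while the change variance becomes (1 − s) + (1 − s·rho²) − 2·rho(1 − s). At rho = 0.5 that is 0.540 + 0.885 − 0.540 = 0.885, and the ratio is 0.783/0.885 = 0.885. With distance in the model the intervals are about 8, 6, 2 and 1% narrower. If selection acts on the baseline score itself (q = 1), the gains are about 5, 3, 1 and 0%.

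**Effect size.** A true difference of 0.40 SD (assumed, equal SDs) reads 0.4/√(2(1 − rho)) = 0.37, 0.40, 0.52, 0.63 on the change SD. On the adjusted residual SD it reads 0.4/√(1 − rho²) = 0.44, 0.46, 0.56, 0.67.

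**The case against.** Three stronger readings are tempting, and the documents support none of them.

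- A reader might infer that the comparison rests wholly on an unadjusted change score. It does not: mixed models are planned for the same outcomes. What remains is that their treatment of baseline is unspecified and that the reported difference is worded as a difference in improvement. The equivalence with the change score also needs separate baseline means, categorical time and complete data. The plan states none of these, and it expects dropout.
- A reader might infer a contradiction, because a t-test or Wilcoxon test cannot carry distance as a covariate. The distance sentence directly follows the mixed-model sentence and reads naturally with it. This is loose wording at most.
- A reader might infer bias. Under randomisation the change score is unbiased.

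The case for leaving the plan alone also has substance. The analyses are exploratory, no sample size or decision rule is tied to them, and the protocol looks mainly to feasibility outcomes and interviews to inform later work. With 48 df, a 95% interval for an SD runs from about 0.83 to 1.25 times its estimate, so a gain of 3 to 14% in interval width is small beside the pilot's own uncertainty. Every magnitude rests on an assumed correlation and SD ratio, and the PHQ-9 cut-off weakens the case for one of the two outcomes. These arguments limit the weight of the point. They do not remove it, because adjustment uses data already collected and its possible cost is bounded and small.

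**Conclusion.** The point holds as a free improvement of low priority. The stated comparison is an unadjusted change score, and the planned mixed model does not by itself secure the gain from baseline adjustment. With 25 per arm, equal SDs and rho from 0.4 to 0.8, adjustment for baseline and distance narrows the 95% interval by about 14% down to 3%. This is most plausible for RMDQ. For PHQ-9, expect roughly half of that or almost nothing. The variance could at worst rise by about 2%, or about 4% with distance, which the plan already intends to include. The figures rest on assumed correlations and SD ratios and on complete, roughly normal data. Nothing here affects validity, and the analyses remain exploratory.

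**What to change.** State in Proposed Analyses that the reported difference, 95% interval and planning variance come from one baseline-adjusted model. Either of these would serve:
- ANCOVA of the follow-up score on arm, baseline score and distance; or
- the planned linear mixed model with a common baseline mean across arms and distance as a covariate, reporting the arm contrast at the chosen visit.

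Keep the t-test or Wilcoxon test as a supporting check, and name the SD used for each effect size.

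A separate wording point can be settled in the same edit: say which assessment the three-month comparison uses, since Outcome Assessments and Data Collection lists "baseline, midpoint (~ 5 weeks), end-point (~ 10 weeks), and 6 months post-intervention".

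The cost is a few sentences of SAP text and a few lines of SAS. No new data are needed.
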